D.3. Setting: Einstein and Montefiore Division of Substance Abuse (DoSA). DoSA is a clinical, research, and teaching division of Einstein's Department of Psychiatry and Behavioral Sciences. DoSA operates a comprehensive substance abuse treatment program providing pharmacotherapy and related services to about 4200 adults (≥ 18 years) with current narcotic addiction (typically heroin). The primary focus is treatment of opiate dependence with methadone, and the average methadone pick-up schedule is 5 times per week. At present, DoSA operates 12 clinics in 5 Bronx communities. The treatment paradigm relies on integrating general and HCV- and HIV-related medical, substance abuse, and mental health services under one roof. Multiple RCTs have been conducted in DoSA. Both recruitment and research visits will occur at DoSA. With [name] (HCV Medical Director), [name] (DoSA Research Director), and [name] (DoSA Medical Director), participant recruitment and private office space for research visits will be ensured.

D.4. Participants. Most DoSA patients are Hispanic (59%) or black (24%), male (62%), and live under the federal poverty line (81%). Mean age is 47 years. Approximately 65% (n=2730) are HCV-infected, and 75% of those have chronic HCV (n=2048); 70% have genotype-1 (n=1434), and 80% of those are HIV-negative (n=1147). We anticipate 800 new admissions over the 3-year recruitment period, representing another 216 HCV-monoinfected genotype-1 patients.

Table 1. Inclusion and Exclusion Criteria (also see Human Subjects)

Inclusion Criteria	Exclusion Criteria

 HIV-negative Willing to receive HCV treatment on-site Initiating treatment with fixed dose (sofosbuvir and ledipasvir) Receiving methadone in clinic at least once per week Age 18 or older Able to provide informed consent English or Spanish speaking 	
 Pregnant or breast-feeding

D.5. Recruitment. Recruitment (as with other successful studies conducted in this setting)^{129,132,142} will be both active and passive; for active recruitment DoSA medical providers will inform genotype-1 HCV-infected subjects about the study and assist with referral, and for passive recruitment subjects will self-refer. Self-referred subjects will meet with their provider to determine whether starting HCV treatment is appropriate.

Determination of eligibility.

Initial screening visit and informed consent:

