Modified directly observed treatment (mDOT). Since DOT of HCV medications will be linked to methadone visits, the number of directly observed oral doses will vary based on the number of days the patients attends the clinic to receive directly observed methadone (pick-up schedule). This intervention is considered modified DOT (mDOT) since only 1-6 out of up to 24 weekly oral medication doses will be observed. Subjects in the mDOT arm will receive: 1) 1 to 6 directly observed oral medication doses per week at the same time as they receive methadone, and 2) individually packaged take-home doses for self-administration on days not in the clinic. In addition, methadone clinic nurses will: 3) notify clinicians when doses are declined, 4) assess for side effects using a standard script; and 5) refer subjects to onsite clinicians as necessary. Since some medications must be taken with food, subjects will also be provided with a high-fat snack (20 grams of fat) when necessary.

Concurrent group treatment (CGT). We developed this model by adapting models linking HCV support groups with treatment^{70,77-78} and models of group medical visits across many chronic conditions.¹⁸⁰⁻¹⁸² Weekly CGT meetings will have 6 components: 1) brief physical exams; 2) psychosocial support from peers and providers; 3) education; 4) direct administration of pegylated interferon medication in the group setting (if applicable); 5) side effect management; and 6) closing meditation on positive health. Six to 12 patients will receive treatment concurrently. Other intervention elements will be as follows.

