FREQUENCY OF CGT CYCLES. New cycles begin at each of 3 sites 3 times per year; therefore there is a new cycle starting nearly every month. To facilitate rapid entry into a group, trial subjects may elect to wait until a cycle is starting at their “home” clinic site, or travel to a different site. In addition, they may join a group that is already in its first month. (Appendix C for group treatment protocols)

D.9. Specific study design considerations.

D.9.2. Why not include an off-site treatment by referral arm? Our study is urgently needed because off-site referral is the current prevailing model of HCV care, and alternative approaches are needed. [name] has studied outcomes from Montefiore’s liver clinic and found that only 15% were eligible for HCV treatment, and SVR rates for genotype-1 were 14% (compared to 40% in our on-site cohorts).¹³ These suboptimal outcomes on referral from our methadone clinics to our liver clinic motivated us to develop our on-site treatment program, in collaboration with [name].

D.9.3. Why another study of DOT for HCV treatment? To date, no HCV DOT study has demonstrated improved virological outcomes, the most important clinical outcome. Our currently funded study has a heterogeneous population and was powered for adherence, not virological outcomes. This study demonstrates that there is increased adherence with DOT and is the foundation for the proposed trial.

D.9.4. Why use weekly blister packs instead of the standard packaging? Weekly pill boxes and blister packs have been shown to be associated with increased adherence and improved virological outcomes.¹⁴⁷⁻¹⁴⁹ The proposed design will maximize adherence in the control arm and eliminate the chance that suboptimal packaging could be responsible for any effect of the intensive interventions. Since any increase in adherence from blister packaging will be observed in all three arms, it will not contaminate intervention effects.

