D.11. Analytic plan. First, the success of randomization will be checked by comparing the mDOT, CGT and TAU groups on key variables, such as age, gender, ethnicity, race, HCV viral load, HCV subtype (1a vs. 1b), BMI, psychiatric history, active drug use, and social support.⁴⁶ By design, IL28B and stage of liver disease will be represented equally in each arm. Continuous variables will be compared between arms using the ANOVA or Kruskal-Wallis test, and categorical variables will be compared using chi-square or Fisher's exact tests. Variables that are not equally distributed will be included in multivariate models. In primary analysis, we will use the intention-to-treat principle, which preserves the advantages of a randomized design.

D.12.1. Hypotheses for Aim 1. We hypothesize that in the intensive intervention arms, compared to the control arm, rates of adherence, treatment completion, and SVR will be significantly higher, and that rates of resistance will be lower. We further hypothesize that the proportion of subjects in the intensive models of care arms who achieve an SVR will be equivalent to that observed in large registration trials.

D.12.2. Analytic plan for Aim 1. Adherence to DAAs, ribavirin, and IFN will be determined using electronic monitors and self report, as described above. Initially, adherence will be calculated as a single outcome for each subject, evaluated at the end of the study. We will use Chi-square tests or Fisher's exact test to compare the proportion of subjects who achieve high adherence rate ($\geq 80\%$) complete treatment, achieve SVR, and develop resistance in the three arms (mDOT, CGT, and TAU). If the omnibus equality test of adherence across the 3 groups is rejected, we will conduct the following 2 specific post-hoc pairwise tests with a Bonferroni adjusted 2-sided alpha= 0.025: mDOT vs. control, and CGT vs. control. This strategy will be applied to multivariable logistic regressions if any potential confounding variables not equally distributed between the study arms at baseline are identified.

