For the analysis of repeatedly measured adherence (using 6 post-baseline time points and adherence as a continuous measure), we will apply mixed effects linear model to test if the 3 groups are significantly different. This model accounts for within-subject longitudinal outcome correlation by taking the subject-level intercept as random. The model will include potential confounding variables. If the omnibus equality test is rejected, we will conduct the 2 post-hoc pairwise tests described above. Concerning potential clustering effects in the CGT arm, we used pilot data (5 groups) to examine whether clustering influenced adherence. Between cluster variation was not significant, as tested by application of a random effects repeated-measure ANOVA model. Clustering in the GCT arm will be minimal, and we will not adjust for it in statistical or power analysis.

We will also apply mixed effects logistic regression to test the significance of mDOT and CGT on repeatedly-measured undetectable HCV VL throughout the intervention period, adjusting for substance use. Changes in illicit drug use will be analyzed using urine toxicology data from each visit, counting the “person-month” as a unit of analysis, and analyzing the proportion of person-months that are positive for use of illicit drugs using a chi-square analysis.

As secondary analyses, we will examine if mDOT and CGT effects, v. TAU, will be mediated by IMB components. We will assess IMB model mediators of adherence at baseline, and during the intervention, and will analyze changes in those variables from the baseline to the intervention period. The indirect effects of IMB mediators will be tested by assessing changes in coefficients of the intervention effect (mDOT or CGT) with and without IMB component(s) in mixed effects models. Confidence intervals of the mediated effects will be calculated by bootstrapping, and mediation assumed if confidence intervals do not include zero.

D.12.3. Hypotheses for Aim 2. We hypothesize that only a minority (~20%) of IDUs will develop resistance, and that the relationship between adherence and resistance will be quadratic.

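### The plan rules out any adjustment for group clustering in the CGT arm on the strength of one non-significant 5-group pilot test, which cannot show that clustering is minimal; the harm is probably small, and a cluster-adjusted companion analysis is a cheap safeguard

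*Combined protocol and SAP*

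**What the plan says.** Section D.12.2 raises possible clustering in the CGT arm and answers it with pilot data from 5 groups: "Between cluster variation was not significant, as tested by application of a random effects repeated-measure ANOVA model". It then concludes: "Clustering in the GCT arm will be minimal, and we will not adjust for it in statistical or power analysis" (GCT is evidently CGT). It gives no ICC, interval or p-value, and the pilot outcome tested was adherence.

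The planned longitudinal adherence model has one random effect, at participant level: "This model accounts for within-subject longitudinal outcome correlation by taking the subject-level intercept as random". It has no group term, and no sensitivity analysis for clustering is planned. The only ICC considered in section D.13 is the within-subject one.

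CGT v. TAU is one of two planned pairwise comparisons, each at two-sided 0.025, behind a gate: "If the omnibus equality test of adherence across the 3 groups is rejected, we will conduct the following 2 specific post-hoc pairwise tests".

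On group size, section D.8.1 says "Six to 12 patients will receive treatment concurrently", and on timing, "New cycles begin at each of 3 sites 3 times per year; therefore there is a new cycle starting nearly every month". Neither statement says how many members of a group will be trial participants.

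**The concern.** CGT participants start treatment together and share weekly meetings, peers and providers. Peer and group support is part of how the intervention is meant to work, so some correlation of outcomes within a group is plausible. TAU and mDOT have no such structure.

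If the correlation is positive and several trial participants share a group, the variance of the CGT mean is understated and the CGT v. TAU test rejects too often. The plan rules out adjustment for every outcome on the basis of one non-significant test of one outcome. Failure to reject with 5 groups is weak evidence of absence. Without a record of who was in which group, the question could not be reopened later.

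**Working it through.** **1. The plan's own power figures (no clustering).** Three-arm chi-square, 40 per arm, omnibus alpha 0.05 (assumed; not stated). Noncentrality is 40 × Σ(p − p̄)² / [p̄(1 − p̄)].
- Adherence 80/80/50%: 40 × 0.06 / 0.21 = 11.43, power about 86.6% (stated: above 87%).
- SVR 70/70/40%: 40 × 0.06 / 0.24 = 10.0, power 81.5% (stated: above 80%).
- Completion 85/60/50%: 40 × 0.065 / 0.2275 = 11.43, power about 86.6% (stated: above 80%).

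The stated figures are reproduced, adherence to within half a point.

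**2. What the pilot test could detect.** Pilot group size is not given. Section D.1.5 reports 39 CGT patients and the 2 × 2 pilot table shows 13 + 11 = 24, so 5 groups would average 7.8 or 4.8. In a one-way random-effects F test on subject means, the F ratio is inflated by 1 + m × ICC / (1 − ICC), where m is group size. For m = 7.8 and ICC 0.05 this is 1.41. The critical value F(4, 34) is 2.65, so power is P(F > 2.65 / 1.41), about 14%.

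| Assumed ICC | Power, 4.8 per group | Power, 7.8 per group |
|---|---|---|
| 0.05 | 10% | 14% |
| 0.10 | 15% | 25% |
| 0.20 | 30% | 48% |

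Even an observed F of exactly 1 would leave a 97.5% upper limit for the ICC of about 0.61 (4.8 per group) or 0.49 (7.8 per group). The pilot leaves the ICC unknown.

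**3. Trial participants per group.** Section D.8.1 gives 3 sites × 3 cycles = 9 cycles a year. Section D.4 gives the recruitment period: "We anticipate 800 new admissions over the 3-year recruitment period". That makes 27 cycles, and 50 / 27 = 1.85 CGT participants per cycle if they spread evenly. If trial participants alone filled groups of 6 to 12, there would be about 4 to 8 groups.

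**4. Error of the unadjusted CGT v. TAU test.** The CGT design effect is DE = 1 + (m − 1) × ICC, where m now counts trial participants per group. With equal arms, the true two-sided error of a nominal 2.5% test is about 2 × P(Z > 2.241 / √[(1 + DE) / 2]).
- m = 2, ICC 0.05: DE 1.05, error 2.7%.
- m = 6, ICC 0.05: DE 1.25, error 3.5%.
- m = 12, ICC 0.10: DE 2.10, error 7.2%.

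Simulation with 50 in TAU agrees (before the gate; the chi-square column sets CGT and TAU both at 50% reaching 80% adherence; values repeat to about 0.1 point):

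| Groups × size | ICC 0.05: continuous / chi-square | ICC 0.10: continuous / chi-square |
|---|---|---|
| 25 × 2 | 2.7 / 2.3% | 2.9 / 2.5% |
| 8 × 6 | 3.5 / 3.2% | 4.6 / 4.4% |
| 6 × 8 | 3.8 / 3.7% | 5.4 / 5.3% |
| 5 × 10 | 4.3 / 3.9% | 6.3 / 5.9% |
| 4 × 12 | 4.7 / 4.6% | 7.3 / 7.2% |

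Fisher's exact test, which the plan also allows, gives 2.4 to 3.5% and 3.4 to 5.8% at 6 to 12 per group. At ICC 0.01 the continuous test stays at 2.6 to 3.0%.

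**5. Does the omnibus gate protect?** Little, if mDOT works. With an mDOT effect of 0.6 SD, gated error for continuous adherence at 6 to 12 per group is 3.4 to 4.8% (ICC 0.05) and 4.5 to 7.2% (ICC 0.10). If all arms are equal it is 2.9 to 3.9% and 3.8 to 6.3%.

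**6. SVR and omnibus power.** With all arms at 95% SVR and 6 to 12 per group, gated chi-square error is 1.5 to 2.2% (ICC 0.05) and 2.1 to 3.4% (ICC 0.10). Exact 95% interval coverage for CGT SVR is 94.6 to 98.0%. Shrinking the CGT arm to 40 / DE lowers omnibus adherence power to 80.9% at worst (12 per group, ICC 0.10). Completion is more exposed, because CGT carries most of its assumed effect: at 12 per group it falls to 73.6% (ICC 0.05) or 63.1% (ICC 0.10), but at 1.85 per group it stays near 85%.

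**The case against.** The strongest reply is that the plan's own schedule points to the harmless case. Filling 27 cycles with 6 to 12 patients takes 162 to 324 people, so 50 trial participants would be a minority in most groups, and the section on group size speaks of patients, not trial subjects. This largely stands: 6 to 12 trial participants per group is the extreme. It is not conclusive. In the pilot, 34 of 39 CGT patients were study participants. Section D.8.1 also lets participants choose their timing ("To facilitate rapid entry into a group, trial subjects may elect to wait until a cycle is starting at their" home site), travel to another site, or join a group late, so an even spread is not assured. Nor does the plan rest its rule on this argument; it rests it on the pilot test.

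A second reply concerns the remedy. Groups start treatment together, and section D.9.6 moves all new enrolees to ledipasvir/sofosbuvir after October 2014, so regimen varies largely between CGT groups. A CGT-only group effect with no regimen term would read that shift as clustering. In simulation with no true group effect, one third of participants on the older regimen, 6 groups of 8 and an assumed 0.5 SD regimen difference in adherence, such a model had error near 1% and power of 55%, against about 74% unadjusted. This stands, and it is why the fix needs a regimen or period term.

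A third reply is cost. With few groups, adjustment loses real power, so replacing the planned model outright is a debatable trade. This also stands; the adjusted result belongs beside the planned one.

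A reader might infer that the CGT v. TAU comparison is materially inflated, or that the SVR result and stated power are undermined. The documents support neither inference. They give no ICC and no count of trial participants per group, and the effects on SVR near 95% and on omnibus adherence power are small. The 95% case does assume that rate in every arm, whereas only 100 of 150 participants are planned for that regimen; the mixture was not evaluated.

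**Conclusion.** The reasoning behind the no-adjustment rule does not hold: a test with roughly 10 to 25% power cannot establish that clustering is minimal, and it says nothing about completion or SVR. Nothing elsewhere in the documents repairs this.

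The practical harm is conditional. At about 2 trial participants per group, the case the schedule suggests, error is 2.6 to 2.9% against 2.5%, which is negligible. If participants concentrate in groups of 6 to 12, error in the CGT v. TAU adherence test is about 3.2 to 4.8% at ICC 0.05 and 4.5 to 7.4% at ICC 0.10. These figures rest on an assumed ICC, assumed pilot group sizes and, for the gated results, an assumed omnibus alpha of 0.05. This is a cheap improvement to the plan, not a flaw that invalidates the trial.

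**What to change.** - Record the group each CGT participant joins. Later adjustment is impossible without it.
- Delete the statement that clustering will be minimal and will not be adjusted for.
- Beside the planned adherence and completion comparisons, prespecify a cluster-adjusted analysis: a random group effect in the CGT arm only (or group-level variance), small-sample degrees of freedom such as Satterthwaite, and a regimen or enrolment-period term in all arms. Keep it whatever the p-value of the group effect.
- Report the group ICC with its interval and the number of trial participants per group.
- Do not call a CGT v. TAU adherence effect robust if it holds only when clustering is ignored.
- A cluster-adjusted interval for CGT SVR is optional.

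The cost is one recorded variable, some analysis work, and a less precise adjusted comparison if groups are few. For continuous adherence (0.6 SD, alpha 0.025, 48 to 50 per arm, ICC 0, no regimen effect), power is 76 to 77% unadjusted, 75% adjusted with 25 groups of 2, and 62 to 69% adjusted with 4 to 8 groups. At ICC 0.05, adjusted power is 74% and 49 to 64% respectively. The planned analysis is retained, so its power is unchanged.

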
 Obtain oral consent for brief screening using Einstein Committee on Clinical Investigations (IRB) screening consent template Brief screen in private room in methadone clinic to determine eligibility Discuss study procedures, risks and benefits of study participation Obtain written consent for 1) clinical trial participation; 2) study staff to use protected health information from methadone clinic records; 3) study staff to disclose protected health information in event of psychiatric distress
Methadone clinic chart review:

 Laboratory test results: HCV Ab, HCV viral load, HIV (within 1 year), HCV genotype/subtype, IL28B, APRI and FibroSURE (biomarker tests for liver fibrosis) Methadone clinic attendance and dose
Second screening visit (medical eligibility determination by [name]):

 Review of HCV-related labs (as above) and fibroscan or liver biopsy (if available) Review of HCV Treatment Evaluation Flow Sheet to confirm no previous HCV treatment and planned on-site treatment regimen: fixed dose (sofosbuvir and ledipasvir) Participants who meet all eligibility criteria scheduled for a baseline visit Randomization (stratified, blocked) generated by centralized computer program

D.6. Participant tracking and retention. We have extensive experience following HCV- and HIV-infected drug users in studies. In our ongoing RCT of directly observed HCV treatment, 24 week follow-up was 92%.¹²⁹ In our completed RCT of directly observed HAART, 24-week follow-up was 86%.¹⁴² At enrollment and subsequent visits, we will record: 1) participants' address, phone number, and social security number; 2) contact information of family or friends; 3) contact information of participants' community-based organizations; 4) contact information of case managers; and 5) locations where participants "hang out".

D.7. Randomization. We will recruit 150 patients (100 on fixed-dose sofosbuvir and ledipasvir), with patients randomized to mDOT, CGT, or TAU in a 1:1:1 ratio (50 subjects in each group) in variable block sizes of 3-6 via central, computer-generated randomization. Two special randomization strategies (stratification and blocking) will be used to avert imbalances in prognostic factors, and to ensure comparison

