Adherence to all medications will be evaluated by electronic monitors and self-report. Weeks on treatment will be determined by electronic monitors and chart review. HCV viral load, virological endpoints, and resistance results will be obtained by chart review and blood draw, if unavailable by chart review. IMB model mediators will be assessed at weeks 8 and 12. Potential moderators will be assessed at each monthly visit.

Table 3. Overview of Data Collection by Aims

Aim & Hypothesis	Construct	Measure, source	Research visit (week)	Source
Outcome Measures				
Aim 1, H1	Adherence	Med-ic® and MEMS® Electronic Monitors	4,8,12	Electronic
Aim 1, H2	Completion	Medical record	NA	Chart
Aim 1, H3	Viral load (SVR)	HCV VL by Roche TaqMAN assay	0,4,8,12, 24, FU 4, FU12, FU24	Chart, Blood
Aim 1/2, H4	Resistance	HCV GenoSURE NS3/4A, NS5A, NS5B (Monogram)	4, 8, 12, 24, FU4, FU12, FU24	Chart, Blood
Aim 3	Cost	HCV treatment mDOT and CGT interventions Non-HCV treatment health services	NA NA 12,24, FU4, FU12, FU24	Chart Logs, Direct Observation Q
Other covariate measures*				
All	Demographics	Age, race/ethnicity, education, income, housing	0	Q
All	HCV-related clinical information	HCV VL, HIV, HCV genotype/subtype, IL28B, APRI and FibroSURE (biomarkers of liver fibrosis)	0	Chart
All	Substance use	Addiction severity Index-Lite (ASI-lite) (152,153) Alcohol use (AUDIT) (154) Urine toxicology EMIT assay	0,4,8,12, 24, FU4, FU12, FU24	Q, Urine
All	Methadone dose opiate withdrawal	Methadone dose; Subjective and Objective Opiate Withdrawal Scales (SOWS and OOWS) (155)	0,4,8,12, 24, FU4, FU12, FU24	Q
All	Neuropsychiatric	MINI (138-140)	0	Q
All	Information, motivation, and behavioral Skills	Health Beliefs Model (161) HCV Motivation (161) Adherence Self-Efficacy (161)	0, 12	Q
All	Social support	Medical Outcomes Scale (162)	0,4,8,12,24, FU4, FU12, FU24	Q
All	DAA levels	GC-MS (if additional funding obtained)	4	Blood
All	Depression, anxiety, and hostility	Depressive symptoms (BDI-II) (156-157) Brief Symptom Inventory (BSI) anxiety subscale (158) BSI hostility subscale (158-160)	0,4,8,12,24, FU4, FU12, FU24	Q
All	Psychosocial factors	Stages of readiness for HCV treatment (183) Trust in physician (184)	0 0,4,8,12,24, FU4, FU12, FU24	Q
All	Quality of life	HCV QOL and EQ-5D (163-166)	0,4,12, 24, FU4, FU12, FU24	Q
All	Med side-effects	Adult ACTG adherence instrument – revised (167)	0,4,8,12, 24, FU4, FU12, FU24	Q

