We will use the model to assess the cost-effectiveness of the 3 interventions: TAU, mDOT, and CGT. Primary outcomes will be projected life-expectancy, quality-adjusted life-expectancy (QALYs), lifetime costs, and incremental cost-effectiveness ratios measured in \$/QALY. We will forecast health and cost outcomes of each intervention for a hypothetical cohort of HCV patients using baseline study data on fibrosis, age, sex, and alcohol use, and study outcome data for each intervention including SVR, resistance, and retention in care. We will explore the potential impact of resistance mutations by varying the efficacy of subsequent HCV retreatment for patients with resistance who choose to be retreated. Lifetime costs will include the costs of the intervention received as well as projected future costs of HCV care depending on treatment effectiveness. Incremental cost effectiveness ratios will be calculated for TAU compared to no treatment and for mDOT and CGI compared to the next most expensive intervention, with costs and QALYs discounted at 3% annually according to standard practice.¹⁷³ The resulting ratios will be compared to a threshold of \$100,000 per QALY.¹⁷⁴⁻¹⁷⁵ To explore uncertainties in our results, we will perform one and 2-way sensitivity analyses on key input variables (e.g. probability of SVR and intervention cost) and probabilistic sensitivity analyses (PSAs) using second order Monte Carlo simulation on multiple variables.¹⁷⁶ For PSAs we will perform 1,000 simulations of a cohort of 100,000 individuals. The result will be a distribution of 1,000 model-based outcomes with a median and interquartile range that reflects underlying uncertainty in critical model parameters.

D.13 Power considerations Assuming a conservative attrition rate of 20%, 50 subjects per arm will begin the study, but 40 subjects per arm will complete it. For power calculations for repeatedly measured continuous or binary adherence outcomes, we will use the expected number of observations per subject. The power analysis is conducted based on the omnibus testing of equality across the three groups. It follows that at least one of the post-hoc pair-wise tests is powered to be rejected by this study design.

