Adherence. Based on our pilot data, if we conservatively assume that 80% of subjects in both mDOT and CGT arms will achieve $\geq 80\%$ adherence (v. 50% in the TAU arm), we will have $> 87\%$ power to find a statistically significant difference. With the application of mixed-effects logistic regression to the repeatedly measured binary adherence outcome, power will be greater than 87% no matter how large the within-subject outcome correlation or intraclass correlation (ICC).

In our previous DOT study, mean adherence in the mDOT group was 87% (SD=12%, n=21), and mean adherence in the TAU group was 77% (SD=20%, n=19) which translates into a standardized effect size or Cohen's $d = 0.6$. Based on this effect size, the power of the mixed effects linear model for the repeatedly measured continuous adherence outcome will be greater than 90%, even if anticipated ICC is as high as 0.5.

Treatment completion. Based on our pilot data, if we assume treatment completion rates of 85% in CGT, 60% in mDOT, and 50% in TAU, we will have $> 80\%$ power to detect this difference.

SVR. We anticipate that SVR rates in the mDOT and CGT arms will be 70%, and $\leq 40\%$ in the TAU arm.^{13,70,82} The statistical power will be $> 80\%$. These are conservative estimates of effect sizes, as actual effect sizes will likely be larger because regimens now contain telaprevir which is taken 3x daily. Effects size for fixed-dose (ledipasvir and sofosbuvir) is likely to be lower.

Resistance. We estimate that 16% of intervention arm subjects v. 30% of TAU subjects will develop resistance. We are underpowered to detect this difference, and consider this an exploratory analysis.

Effectiveness of intensive models of care. We will determine the proportion (and 95% CI) of subjects in each of the intensive intervention arms to achieve SVR, and compare to results from large registration trials.

D.14. Limitations. In addition to the considerations noted in Section D., our results may not be generalizable to HCV-infected drug users not enrolled in methadone clinics. However, we believe that the intensive models we are testing, if efficacious, can and should be adopted in diverse settings and populations.

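### Week-0 HCV viral load reaches the virological analyses only if it happens to be imbalanced between arms; pre-specifying it as a covariate is a cheap improvement whose power gain the documents cannot pin down

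*Combined protocol and SAP*

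**What the plan says.** **Measurement.** The SVR row of Table 3 gives the measure as "HCV VL by Roche TaqMAN assay", taken at week 0 and at every later visit. Viral load is listed again in the same table as a week-0 clinical covariate from the chart. D.10.4 adds that the assay will be run on study blood where the chart has no result, so a week-0 value should exist for every participant.

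**Outcome.** D.10.3 defines SVR as an undetectable viral load 12 weeks after treatment ends.

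**SVR analysis.** D.12.2 compares the three arms by chi-square or Fisher's exact test. If the omnibus test rejects, two pairwise tests against control follow at two-sided 0.025. Multivariable logistic regression is used only when potential confounders are found to be unevenly spread at baseline. This repeats the rule in D.11, which names viral load among the variables to be checked: "Variables that are not equally distributed will be included in multivariate models".

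**Repeated viral load.** D.12.2 also plans a mixed-effects logistic regression of "repeatedly-measured undetectable HCV VL throughout the intervention period, adjusting for substance use". The nearby statement that potential confounders will be included belongs to the linear mixed model for adherence, not to this one.

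**Power.** D.13 states: "50 subjects per arm will begin the study, but 40 subjects per arm will complete it". For SVR it states: "We anticipate that SVR rates in the mDOT and CGT arms will be 70"%, against at most 40% in the control arm, with power above 80%.

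**The concern.** In a randomised trial, baseline differences between arms arise by chance. Whether a variable is imbalanced says nothing about whether it predicts the outcome, so a balance test is a poor way to choose covariates. A prognostic variable that happens to be balanced is left out, and a non-prognostic one that happens to be imbalanced is put in.

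Two things are at stake. First, the form of the SVR analysis is not fixed in advance: nobody can say before the data are seen whether it will be an unadjusted test or an adjusted regression, or with which covariates. D.11 gives no threshold for imbalance, which widens the uncertainty. Second, if week-0 viral load is prognostic, leaving it out gives up power on the outcome that D.9.3 treats as clinically the most important, when the planned SVR power is only a little above 80%.

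**Working it through.** **Inputs from the documents.** SVR 70%, 70% and 40%; 50 randomised and 40 completing per arm (D.13); 1:1:1 allocation (D.7); a three-group omnibus test (D.13); pairwise two-sided alpha 0.025 (D.12.2).

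**Assumptions.** Omnibus alpha 0.05, which is not stated. The correlation rho between week-0 log10 viral load and SVR is also not stated, so 0.1 to 0.5 is shown.

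**Step 1: reproduce the planned power.**
Mean rate = (0.70 + 0.70 + 0.40)/3 = 0.60.
Sum of squared deviations = 0.01 + 0.01 + 0.04 = 0.06.
Noncentrality = n × 0.06/(0.60 × 0.40) = 40 × 0.25 = 10.0.
Power of the 2-df chi-square test = 81.5% (binomial simulation 82.0%). This agrees with the stated figure of above 80%.

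**Step 2: add the covariate.** Adjustment is approximated as a variance reduction of (1 − rho²), so the noncentrality becomes 10/(1 − rho²).

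| rho | Noncentrality | Power, 40 per arm | Gain (points) |
|---|---|---|---|
| 0 | 10.00 | 81.5% | – |
| 0.1 | 10.10 | 82.0% | 0.4 |
| 0.2 | 10.42 | 83.2% | 1.6 |
| 0.3 | 10.99 | 85.2% | 3.7 |
| 0.4 | 11.90 | 88.1% | 6.5 |
| 0.5 | 13.33 | 91.5% | 10.0 |

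**Step 3: cross-check by simulation.** An adjusted logistic likelihood-ratio test was set against the unadjusted chi-square, with 40 per arm and 4,000 trials per setting. Power rose from 82.1% to 84.8% at rho about 0.28, from 82.8% to 89.2% at about 0.38, and from 83.3% to 92.5% at about 0.48. The approximation is adequate. In a separate simulation the adjusted test rejected 5.1% of the time under the null.

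**Step 4: all 50 per arm analysed.** Noncentrality = 50 × 0.25 = 12.5 and power is 89.6%. It rises to 92.3% at rho 0.3 (+2.7) and 96.4% at rho 0.5 (+6.7).

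**Step 5: near the ceiling.** D.9.6 cites SVR above 95% for the regimen that all new enrolees receive, and D.13 expects a smaller effect with it. Neither gives rates by arm, so the rates below are assumed, with 40 per arm.

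| Assumed SVR | Unadjusted | rho 0.3 | rho 0.5 |
|---|---|---|---|
| 95/95/90% | 13.9% | 14.9% | 17.2% |
| 95/95/85% | 36.8% | 40.0% | 47.4% |

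The last column is generous. For a normally distributed covariate and a binary outcome with a 95% rate, the largest possible correlation is φ(1.645)/√(0.95 × 0.05) = 0.103/0.218 = 0.47, where φ is the standard normal density. A correlation of 0.5 therefore cannot occur in those arms.

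**Step 6: repeated undetectable viral load.** The documents give no rates, intraclass correlation or power for this model, so no gain can be calculated from them.

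**The case against.** The strongest reply is that nothing here is wrong. An unadjusted intention-to-treat comparison of proportions is valid and reaches its stated power; covariate adjustment only makes it more efficient. That stands, and it limits the point to an improvement.

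The size is also open to challenge. At an SVR of 60%, rho 0.3 needs an odds ratio of about 2.0 per standard deviation of viral load (SVR about 72% against 48% in the better and worse halves), and rho 0.5 needs about 4.0 (81% against 39%). The documents neither support nor exclude such associations. At rho 0.2 or less the omnibus gain is under 2 points.

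A reader might infer that week-0 viral load is the baseline value of the outcome and so must correlate strongly with it. It is not: the outcome is binary, and participants with chronic HCV should nearly all be detectable at week 0. Log10 viral load is a separate candidate prognostic variable.

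A reader might also infer that the covariate would enter in about 1 trial in 20. That assumes a 5% balance test. D.11 sets no threshold, and a 20% threshold would give 1 in 5.

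Finally, D.7 already stratifies on IL28B genotype and cirrhosis, the factors it considers historically important for virological outcome, so part of prognosis is balanced by design. What viral load adds beyond them is unknown. But balancing two other factors does not make imbalance a sound rule for choosing the rest.

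**Conclusion.** The point holds as a cheap improvement. The documents collect week-0 viral load and call it a key variable, pre-specify it in neither virological analysis, and leave its use to chance imbalance. That weakness in the rule does not depend on any correlation.

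The power gain does. For the SVR omnibus test at the planned rates with 40 per arm, it runs from 0.4 points (rho 0.1) to 10.0 points (rho 0.5). At rho 0.3 to 0.5 it is about 4 to 10 points with 40 per arm and about 3 to 7 with 50. Over the same correlations it is about 1 to 3 points at an assumed 95/95/90%, and about 3 to 11 at an assumed 95/95/85%.

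Two stronger readings are not supported. The first is that the plan forfeits 4 to 10 points of power in both virological analyses: that range needs an undocumented correlation and planning rates that predate the current regimen, and it cannot be carried over to the repeated model. The second is that adjustment would secure adequate power under the current regimen: in both near-ceiling scenarios power stays below 50% with or without it.

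**What to change.** In D.12.2, pre-specify log10 HCV viral load at week 0 as a covariate, whatever the balance check shows, in:

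- **SVR:** a logistic regression on arm and log10 week-0 viral load, with a likelihood-ratio omnibus test for arm. Report standardised risk differences, so that the effect stays on the scale of the planned comparison of proportions.
- **Repeated undetectable viral load:** the planned mixed-effects logistic model, with log10 week-0 viral load added to substance use.

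Keep the chi-square or Fisher result for SVR as a sensitivity analysis. State that a penalised (Firth) fit will be used if SVR failures are few.

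The cost is a few sentences in the analysis plan and no new data. The one downside is that sparse failures, which are likely if SVR is near its ceiling, may make the penalised fit necessary.
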